#### **4.4 MYCOBACTERIAL DISEASES**

4.4.1 *Mycobacterium tuberculosis* – Inactive versus active infection must be distinguished. In patients with low CD4+ counts, 2/3's present with extrapulmonary disease. Diagnosis may require biopsies in addition to culture. There is a high incidence of drug resistant strains. Consultation with the infectious disease service is mandatory for these patients. Combination therapy with isoniazid, rifampin, pyrazinamide, ethambutol and pyridoxine (vitamin B6) is usually initiated. These drugs may cause hepatitis, bone marrow suppression, optic neuritis and peripheral neuropathy. Careful monitoring of toxicities is required if these drugs are given concomitantly with HAART and/or with high-dose methotrexate.

4.4.2 *Mycobacterium avium complex* usually occurs in patients with CD4+ count  $<100/\text{mm}^3$ . Disseminated infection presents with fever, weight loss, night sweats, diarrhea, anemia, neutropenia, and thus may be difficult to differentiate from “B” symptoms. Sputum and blood cultures should be obtained. Clarithromycin or azithromycin in combination with clofazimine or rifampin are recommended.

#### **4.5 TOXOPLASMOSIS**

Patients with concurrent toxoplasmosis will be treated in concert with infectious disease consultation. In patients receiving high-dose methotrexate, sulfadiazine should not be given 48 hours prior to administration of methotrexate administration through completion of leucovorin rescue due its effect on renal excretion of methotrexate, (see Section 3.7) therefore sulfadiazine-sparing regimens are preferred.

#### **4.6 PROPHYLAXIS FOR FEBRILE NEUTROPENIA**

See Sections 3.6.4.1 and 3.9.5 for guidelines on use of filgrastim and antibiotics.

#### **4.7 FEBRILE NEUTROPENIA**

A life-threatening complication requiring hospitalization and urgent broad-spectrum antibiotics.

#### **4.8 ANEMIA**

If symptomatic or if the hemoglobin falls below 8 mg/dL, erythropoietin may be considered. Red blood cell transfusions are sometimes associated with increased HIV replication and opportunistic infections, but if necessary, red blood cell transfusion support should be utilized.

#### **4.9 THROMBOCYTOPENIA**

Should be treated conservatively. In the absence of bleeding or a planned invasive

procedure, platelet transfusions should be given for a platelet count below 10,000/mm^3. If invasive procedures (including lumbar puncture) are planned or the patient develops bleeding, platelet transfusions should be administered in accordance with standard of practice, usually maintaining a platelet count >50,000/mm^3.

#### **4.10 CENTRAL VENOUS ACCESS**

If peripheral access not feasible for a patient, temporary lines are preferred (removed after completion of each infusion) and include: internal jugular line; PICC lines via the brachial vein. Other lines include semi-permanent HICKMAN, GROSHONG catheters or medi-port implanted devices. All devices will have nursing supervision to include patient self-care and cleaning/flushing of the devices.

#### **4.11 IMMUNE RECONSTITUTION INFLAMMATORY SYNDROME (IRIS)**

IRIS will be defined using AIDS Clinical Trial Group (ACTG) 2009 Criteria, using the following criteria:

4.11.1 Initiation, reintroduction or change in antiretroviral therapy/regimen or therapy for opportunistic infections (OI).

**AND**

4.11.2 Evidence of:

4.11.2.1 An increase in CD4+ cell count as defined by  $\geq 50$  cells/mm^3 or a  $\geq 2$ - fold rise in CD4+ cell count, and/or

4.11.2.2 Decrease in the HIV-1 viral load of  $>0.5 \log_{10}$  and/or

4.11.2.3 Weight gain or other investigator-defined signs of clinical improvement in response to initiation, reintroduction or change of either antiretroviral therapy/regimen or OI therapy.

**AND**

4.11.2.4 Symptoms and/or signs that are consistent with an infectious or inflammatory condition.

**AND**

4.11.2.5 These symptoms and/or signs cannot be explained by a newly acquired infection, the expected clinical course of a previously recognized infectious agent, or the side effects of medications.

**AND**

4.11.2.6 The infectious/inflammatory condition must be attributable to a specific pathogen or condition.

Although ACTG IRIS criteria does not explicitly include CNS IRIS due to EBV-associated PCNSL, it is biologically likely that a reconstituted immune system would react to EBV associated antigens in AIDS-PCNSL. As such, patients with neurologic deterioration on therapy who do not meet criteria for progressive lymphoma and have evidence of CNS edema on brain MRI or CT imaging and T-cells in the central nervous system will be managed for CNS IRIS.

All patients with IRIS will be managed with appropriate antibiotics, and steroids. For CNS IRIS, patients can receive up to 1gram of solumedrol (or equivalent) daily for a minimum of 4 days, followed by tapering of steroids. Protocol therapy for AR-PCNSL will not be discontinued due to CNS IRIS, although treatment may be delayed to perform diagnostic studies or in cases with Grade 4 Neurotoxicity at least possibly attributable to CNS IRIS if the PI or LAI determines that treatment delay is clinically indicated to diagnose and treat CNS IRIS.

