3.4.2 High-dose methotrexate

3.4.2.1 The creatinine clearance (CrCl) will be calculated by method of Cockcroft-Gault prior to each cycle (see [Appendix 4](#)). If CrCl is  $\geq 100$  mL/min, then no dose adjustment is necessary. If CrCl is  $< 100$  mL/min, then the methotrexate dose is adjusted by the fraction of CrCl less than 100 mL/min (e.g., methotrexate dose =  $6000 \text{ mg/m}^2 \times \text{CrCl}/100$ ).

3.4.2.1.1 For estimated creatinine clearance  $< 100$  mL/min, a 24-hour urine collection should be obtained *plus* a serum creatinine at the end of the collection period to determine a measured creatinine clearance.

3.4.2.2 Delayed methotrexate serum clearance ( $> 3$  days after methotrexate infusion) may occur and mandates accelerated rescue and continued hydration and alkalinization. The minimum interval between achieving a serum methotrexate level  $\leq 0.05 \text{ mcg/mL}$  and the start of a subsequent treatment cycle is 7 days.

3.4.2.3 For creatinine clearance  $< 60$  mL/min, no methotrexate will be administered. Administer rituximab without methotrexate after discussion with a medically responsible investigator if renal function cannot be expected to be optimized (CrCl  $\geq 60$  mL/min) within 3 days.

3.4.2.4 For transient ALT and/or AST elevations  $\geq 10X$  the upper limit of normal, withhold methotrexate until both ALT and AST are  $\leq 5X$  the upper limit of normal, then permanently reduce methotrexate dosage by 25% for all subsequent cycles beginning with the next cycle.

3.4.2.5 For ANC  $< 1000 \text{ cells/mm}^3$ , delay methotrexate until ANC recovers to  $\geq 1000/\text{mm}^3$ .

3.4.2.6 For platelet counts  $< 50,000/\text{mm}^3$ , delay methotrexate until platelet count recovers to  $\geq 50,000/\text{mm}^3$ .

3.4.2.7 For any other Grade 3 or greater toxicities related to methotrexate, with the exception of hematologic toxicity, hold methotrexate until toxicity abates to Grade  $\leq 2$ .

3.4.2.8 For pulmonary toxicity related to methotrexate, permanently discontinue methotrexate.

3.4.2.9 Note, if toxicity attributed to methotrexate prevents subsequent methotrexate treatment prior to the time of complete response, patient will be considered a treatment failure. Failure of toxicity to resolve and thus creating dose delays in excess of 15 days will result in methotrexate discontinuation.

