### **3.5 CRITERIA FOR DISCONTINUING RITUXIMAB AND HIGH-DOSE METHOTREXATE WITH LEUCOVORIN RESCUE**

- 3.5.1 Completion of therapy
- 3.5.2 Delayed methotrexate clearance due to impaired renal function, requiring glucarpidase
- 3.5.3 Creatinine clearance <60 mL/min based on a 24-hour urine collection that cannot be corrected within 2 weeks
- 3.5.4 Any creatinine clearance <30 mL/min based on 24-hour urine collection.
- 3.5.5 Inability to tolerate required intravenous hydration (minimum 60 hours of intravenous fluid at a rate  $\geq$ 100 mL/hour)
- 3.5.6 Dose delays in excess of 15 days
- 3.5.7 Withdrawal of consent.
- 3.5.8 Inability to administer to HAART or other oncologic therapies.
- 3.5.9 Progressive neurologic symptoms attributed to progressive AR-PCNSL
- 3.5.10 Untreatable concurrent illness
- 3.5.11 Methotrexate with leucovorin rescue may be discontinued, if in the opinion of the PI or LAI, the risk of continued therapy outweighs the potential benefit of continued therapy, or if patient non-adherence interferes with study objectives.
- 3.5.12 Patients who discontinue Rituximab and methotrexate with leucovorin rescue may continue with “Radiation-sparing Best Available Therapy”, including dose-dense Rituximab, if clinically indicated.

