### **3.10 RADIATION THERAPY GUIDELINES**

- 3.10.1 Radiation therapy to the brain will be deferred in all patients unless there is progression of disease with high-dose methotrexate- rituximab, or radiation-sparing best therapy, stable disease or partial response as best response to high-dose methotrexate- rituximab or radiation-sparing best therapy, or recurrence following apparent complete response with high-dose methotrexate- rituximab or

radiation-sparing best therapy, and further chemotherapy approaches by themselves are not assessed by the treatment team to be clinically appropriate. Patients requiring radiotherapy (or any other additional therapy for AR-PCNSL) will be considered treatment failures for this study. Patients requiring such therapy will be returned to the care of the referring physicians when possible. If possible, continuation of neuropsychometric testing outlined in the study will continue, to describe the cognitive outcome.

3.10.2 Radiation following high-dose methotrexate may confer additional risk of neurotoxicity. For this reason, when feasible, salvage chemotherapy strategies will be considered as appropriate.

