## 5.3 RESPONSE CRITERIA

Response criteria are based on published standards for phase II studies of supratentorial malignant glioma and a modification of the response assessment of aggressive non-Hodgkin's lymphoma by integrated international workshop criteria and fluorine-18 – fluorodeoxyglucose positron emission tomography, and an international workshop to standardize baseline evaluation and response criteria for primary CNS lymphoma. Cross-sectional measurements of tumors will be used to assess baseline and responses.

- 5.3.1 Complete Response - disappearance of all enhancing lesions on MRI of the brain, negative FDG-PET scan persisting for at least 4 weeks in patients who were off corticosteroids, negative CSF cytology and neurologically improved from baseline.
- 5.3.2 Complete Response Unconfirmed (CRu) – either a CRu, PR or SD by MRI criteria with a completely negative FDG-PET off steroids, and negative CSF cytology. If there is no evidence of progression while off steroids for 4 months, response will be reclassified as CR.
- 5.3.3 Partial Response
  - 5.3.3.1 A reduction of enhancing tumor volume by more than 50% maintained for at least 4 weeks, steroids stable or reduced, and neurologically stable or improved with positive FDG-PET, or

- 5.3.3.2 Normalization of MRI, negative FDG-PET, but with persistent disease by CSF cytology.
- 5.3.4 Progressive disease - an increase of tumor volume of more than 25% or occurrence of new lesions, or neurologically worse, steroids stable or increased.
- 5.3.5 Stable disease – not meeting the criteria for complete response, partial response, or progressive disease and with a positive FDG-PET
- 5.3.6 Treatment failure - progressive or stable disease, relapse after initial response, death, or discontinuation of chemotherapy because of complications or because of patient's or Investigator's decision. Patients who require radiotherapy will be considered treatment failures for purposes of the protocol, regardless of long-term outcome.
- 5.3.7 Substantial brain dysfunction and cognitive problems (as referred to in sections 1.2.3 and 7.4.4) that will define treatment failure refer to post-treatment recurrent brain lymphoma, treatment related functional brain pathology, and/or neurologic function class 3 or 4 as defined in Appendix 2: Neurological Function Class.

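### Section 5.3.4 scores neurological worsening without steroid reduction as progression, with no exception for the CNS IRIS that section 4.11 is written to manage

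*Combined protocol and SAP*

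**What the plan says.** Section 4.11 sets up a management route for CNS IRIS. It is for "patients with neurologic deterioration on therapy who do not meet criteria for progressive lymphoma" who also have brain edema on MRI or CT and T-cells within the CNS. The steroid course can be heavy: "For CNS IRIS, patients can receive up to 1gram of solumedrol (or equivalent) daily for a minimum of 4 days", then a taper. Chemotherapy goes on: "Protocol therapy for AR-PCNSL will not be discontinued due to CNS IRIS, although treatment may be delayed". The section calls an immune reaction to EBV antigens in this tumor biologically likely.

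Section 5.3.4 defines progressive disease as "an increase of tumor volume of more than 25% or occurrence of new lesions, or neurologically worse, steroids stable or increased". Section 5.3.6 then lists as treatment failure "progressive or stable disease, relapse after initial response, death, or discontinuation of chemotherapy because of complications", among other reasons.

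Three other places matter:

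- Section 3.5.9, on stopping rituximab and methotrexate, uses a narrower test: "Progressive neurologic symptoms attributed to progressive AR-PCNSL".
- Section 3.10.1 says "Radiation therapy to the brain will be deferred in all patients unless there is progression of disease" (or another listed disease outcome). The same sentence adds a second condition: the treatment team must also judge that further chemotherapy alone is not appropriate.
- Sections 1.1.1.1 and 6.1.3 define the primary endpoint as being alive at two years, free of recurrent lymphoma and of severe cognitive problems. Neither cites 5.3.6. Progression-free survival is a secondary endpoint (1.1.2.2), and 6.1.3 treats all secondary endpoints as exploratory.

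**The concern.** Section 4.11 depends on the progression criteria to decide whom it covers, and 5.3.4 is where those criteria stand. One of the alternatives in 5.3.4 is purely clinical. It describes the state that brings a patient to 4.11: worse neurologically, with steroids level or going up. Applied as written, 5.3.4 takes the patient first, and 4.11 is left with those whose steroids were being reduced when they worsened.

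The likely intent is that edema with CNS T-cells and no tumor growth is not progression, but the text does not say so. An assessor who follows 5.3.4 records progression and treatment failure. One who follows the evident purpose of 4.11 records CNS IRIS and continues the cycles. With 15 patients in the main cohort, one such difference is visible in any reported rate or survival curve.

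**Working it through.** **Step 1. Set the definitions against one patient.** Take a patient in induction who deteriorates neurologically with steroids unchanged. Imaging shows edema, with no tumor growth and no new lesion, and T-cells are found in the CNS.

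| Section | Test | Result |
|---|---|---|
| 5.3.4, volume | Increase above 25% | Not met |
| 5.3.4, new lesion | Any | Not met |
| 5.3.4, clinical | Worse, steroids stable or increased | Met; no imaging or attribution needed |
| 4.11 entry | Progression criteria not met | Fails, because 5.3.4 is met |
| 5.3.6 | Progressive disease | Treatment failure |
| 3.5.9 | Worsening attributed to AR-PCNSL | Not met; this rule does not stop therapy |

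Section 3.5.9 contains the attribution test that 5.3.4 lacks, but it governs stopping treatment, not the response category. A patient who worsens while steroids are being reduced does not meet the clinical alternative and can enter 4.11.

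**Step 2. Reproduce the plan's own figure.** Inputs from 6.1.3: n = 15, null 30%, alternative 65%, exact binomial test, one-sided alpha 0.10, stated power 88%.

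- P(X ≥ 7 | 15, 0.30) = 0.1311, above 0.10.
- P(X ≥ 8 | 15, 0.30) = 0.0500, so 8 successes are needed.
- Power = P(X ≥ 8 | 15, 0.65) = 0.887, which agrees with 88%.

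**Step 3. Size of the effect, if it reaches the primary endpoint.** One patient is 1/15 = 6.7 percentage points. At the boundary, one reclassified patient turns 8/15 (p = 0.050) into 7/15 (p = 0.131).

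The rest rests on three assumptions that the documents do not supply: 5.3.6 failure counts as failure of the primary endpoint; k of 15 patients are affected, with k from 0 to 3; and those patients would otherwise succeed at 65%. The expected fraction is then 0.65 × (15 − k)/15, and power is P(X ≥ 8 | 15 − k, 0.65).

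| k | Expected fraction | Power |
|---|---|---|
| 0 | 65.0% | 0.887 |
| 1 | 60.7% | 0.816 |
| 2 | 56.3% | 0.716 |
| 3 | 52.0% | 0.583 |

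**Step 4. The effect that needs no such assumption.** Each patient scored under the clinical alternative of 5.3.4 adds a progression event at the onset of worsening, whatever the tumor later does.

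**The case against.** The strongest reply is that 4.11 and 5.3.4 form an order of precedence: progression is assessed first, and IRIS is considered only if progression is not met. On that view the sections do not contradict each other. This is fair as a description. But the order sends an inflammatory reaction without tumor growth into the progression category, which 4.11 evidently means to prevent.

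Several stronger inferences are tempting, and the objection to each stands.

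- *That 4.11 excludes nearly all its own patients.* Not shown. The background (1.2.2) says high-dose steroids are avoided where possible in advanced HIV disease, so patients on a taper or on no steroids are plausible. Section 5.3.4 does not say whether no steroids counts as stable. Steroids given because IRIS was diagnosed cannot settle whether the entry condition was met beforehand.
- *That a progression label by itself opens radiotherapy.* It does not. Section 3.10.1 also requires the team's judgement on further chemotherapy, and 3.10.2 favors salvage chemotherapy where feasible.
- *That the primary fraction necessarily falls.* The documents tie failure explicitly to the study's statistical purposes or result only for patients needing radiotherapy (3.7) or radiotherapy or other additional therapy (3.10.1). Progression during treatment that later resolves is not named in the primary endpoint.
- *That the label would be chosen once the two-year result is known.* Management under 4.11 is decided at deterioration, before that result exists.
- *That the 15-day limits contradict 4.11.* Section 3.4.2.9 reads "Failure of toxicity to resolve and thus creating dose delays in excess of 15 days will result in methotrexate discontinuation", but it follows a sentence about methotrexate toxicity and may not reach IRIS. Sections 3.5.6 and 3.11.1 name no cause and can be read as a general ceiling on the delays that 4.11 allows. If delay is counted from the scheduled dose (an assumption), a stop needs more than 14 + 15 = 29 days between induction doses. What is missing is a cross-reference.

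**Conclusion.** The gap is real and minor. As written, 5.3.4 scores a patient with the 4.11 imaging and T-cell findings as progressive disease whenever worsening occurs without steroid reduction. That makes the patient a treatment failure under 5.3.6 and closes the 4.11 route.

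The certain consequence is a false event in progression-free survival, which is exploratory. The shift of 6.7 points per patient in the primary fraction holds only if 5.3.6 failure is carried into that endpoint and the patient is well at two years. The table of lowered fractions and power is illustrative: it rests on an assumed 0 to 3 affected patients. Section 6.1.3 does not make rejection of 30% a binding condition for further development, so power matters less than the estimate. If no patient develops CNS IRIS, nothing changes.

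**What to change.** Add to 5.3.4: neurological worsening alone, in a patient with the edema and CNS T-cell findings described in 4.11, is not progression unless at least one of the following holds:

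- tumor volume rises by more than 25%;
- a new lesion appears;
- CSF cytology is positive, where CSF is obtained;
- the worsening has not stabilized or improved by the next scheduled MRI.

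In any of these cases, progression is dated to the onset of worsening. The last condition is needed so that a patient who keeps declining without measurable growth is still scored. Tying the exception to the findings, not to entry under 4.11, removes the circularity.

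Report the number managed under 4.11. Repeat progression-free survival and the primary fraction with all of them scored as events or failures.

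The cost is a few sentences and one extra line for each of two results. Section 4.11 already calls for the edema and T-cell findings, and MRI is already scheduled after cycles 2, 4, 6 and 8 (3.2). The downside is that true progression first labelled IRIS may be recognized only at the next scheduled MRI. Scans are about 4 weeks apart in induction (two 2-week cycles) and further apart in consolidation. Back-dating limits the effect on progression-free survival, and the repeated results show any upward effect.

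As an optional clarification, 4.11 could state whether the 15-day limit in 3.5.6 and 3.11.1 applies to IRIS delays.

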#### **4.12 NUTRITIONAL ASSESSMENT AND PSYCHOLOGICAL SUPPORT**

AR-PCNSL is commonly complicated by malnutrition. Patients with weight loss or evidence of wasting syndrome should have a nutritional consult and nutritional intake should be optimized by either enteral or parenteral means. All patients on the study will be informed of and encouraged to see a NIH Social Worker for evaluation and support.

### **5 DATA COLLECTION AND EVALUATION**

#### **5.1 DATA COLLECTION**

The members of the Retroviral Diseases Section Research Team will collect data.

The PI will be responsible for overseeing entry of data into C3D, an in-house password protected electronic system and ensuring data accuracy, consistency and timeliness. The principal investigator, associate investigators/research nurses and/or a contracted data manager will assist with the data management efforts. All data obtained during the conduct of the protocol will be kept in secure network drives or in approved alternative sites that comply with NIH security standards. Primary and final analyzed data will have identifiers so that research data can be attributed to an individual human subject participant.

All adverse events, including clinically significant abnormal findings on laboratory evaluations, regardless of severity, will be followed until return to baseline or stabilization of event. Patients will be followed for adverse events for 30 days after removal from study treatment or until off-study, whichever comes first.

An abnormal laboratory value will be recorded in the database as an AE **only** if the laboratory abnormality is characterized by any of the following:

- Results in discontinuation from the study
- Is associated with clinical signs or symptoms
- Requires treatment or any other therapeutic intervention
- Is associated with death or another serious adverse event, including hospitalization.
- Is judged by the Investigator to be of significant clinical impact
- If any abnormal laboratory result is considered clinically significant, the investigator will provide details about the action taken with respect to the test drug and about the patient's outcome.

**End of study procedures:** Data will be stored according to HHS, FDA regulations, and NIH Intramural Records Retention Schedule as applicable.

**Loss or destruction of data:** Should we become aware that a major breach in our plan to protect subject confidentiality and trial data has occurred, the IRB will be notified.

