#### 1.1.2 Secondary

1.1.2.1 To describe the acute toxicities associated with administering a regimen of high-dose methotrexate with leucovorin and rituximab with HAART in patients with AR-PCNSL

1.1.2.2 To estimate the complete response rate, progression-free, disease-free, and overall survivals to high-dose methotrexate with leucovorin and rituximab given with HAART in patients with AR-PCNSL

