3.8.2.1.6 Ophthalmologic examination to assess for ocular involvement by lymphoma

3.8.2.1.7 Viral hepatitis studies (not necessary to repeat previously documented positive studies; results not required prior to treatment):

- Hepatitis A
- anti-HAV IgG
- Hepatitis B
- anti-HBsAg
- HBsAg
- Anti-HB core
- Hepatitis C
- anti-HCV

- 3.8.2.1.8 Serum anti-toxoplasmosis antibody titers (not necessary to repeat if already obtained on NIAID protocol)
- 3.8.2.1.9 Syphilis serology (not necessary to repeat if already available within 6 months prior to study entry)
- 3.8.2.1.10 HIV viral load if not available within 14 days prior to enrollment
- 3.8.2.1.11 T-cell subsets if not available within 14 days prior to enrollment
- 3.8.2.1.12 HIV genotype or Virtual Phenotype® to assess for resistant HIV if not previously done
- 3.8.3 Day 1 each cycle; then monthly for 2 months, then every 2 months x3, then every 3 months x6, then every 6 months x 2, then every 12 months x 2 (for patients co-enrolled in 01-C-0038 and followed clinically beyond year 3).

For “Radiation-Sparing Best Available Care” Cohort, scheduled evaluations on Days 1, 8, 15, 21, 28 then monthly for 2 months, then every 2 months for 3 times, then every 3 months of total of 36 months, then yearly for 2 years (for patients followed clinically beyond year 3).

- 3.8.3.1 Physical examination with documentation of abnormalities
- 3.8.3.2 Particular emphasis on neurological examination
- 3.8.3.3 Assign neurologic function class (see [Appendix 2](#))
- 3.8.3.4 CBC with differential (CBC with differential drawn up to 24 hours prior to starting therapy acceptable for patients receiving filgrastim to manage neutropenia)
- 3.8.3.5 Electrolytes
- 3.8.3.5.1 Serum creatinine
  - calculated and/or measured creatinine clearance
  - Whenever the calculated creatinine clearance is <100 mL/min, a measured creatinine clearance should be obtained.
- 3.8.3.5.2 Hepatic panel
- 3.8.3.5.3 Mineral panel
- 3.8.3.6 During treatment cycles until serum methotrexate level  $\leq 0.05$  mcmol/L:
  - 3.8.3.6.1 Blood specimens for methotrexate levels must be drawn at scheduled times
  - 3.8.3.6.2 Hepatic panel every other day
  - 3.8.3.6.3 CBC with differential daily
  - 3.8.3.6.4 Electrolytes, creatinine, BUN daily
- 3.8.4 Baseline Staging
- 3.8.4.1 MRI: if done within 2 weeks before study entry, repeat only if interval clinical deterioration has occurred

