### 8.2.2 NCI-IRB Requirements for PI Reporting at Continuing Review

The protocol PI will report to the NCI-IRB:

1. A summary of all protocol deviations in a tabular format to include the date the deviation occurred, a brief description of the deviation and any corrective action.
2. A summary of any instances of non-compliance
3. A tabular summary of the following adverse events:
  - All Grade 2 **unexpected** events that are possibly, probably or definitely related to the research;
  - All Grade 3 and 4 events that are possibly, probably or definitely related to the research;
  - All Grade 5 events regardless of attribution;
  - All Serious Events regardless of attribution.

**NOTE:** Grade 1 events are not required to be reported. Also, as noted in section 8, reporting is required only for events while on-treatment and for 30-days after the last dose of therapy.

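### Section 5.1 has no severity criterion for recording laboratory abnormalities as adverse events, so a toxicity summary drawn from AE records may undercount severe laboratory toxicity

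*Combined protocol and SAP*

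**What the plan says.** The acute-toxicity objective is secondary and descriptive: "To describe the acute toxicities associated with administering a regimen of high-dose methotrexate with leucovorin and rituximab with HAART" (Section 1.1.2.1). Section 5.4 adopts CTCAE version 3.0 for grading.

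Section 5.1 sets the recording rule: "An abnormal laboratory value will be recorded in the database as an AE", restricted to values that meet at least one of these conditions:

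- "Results in discontinuation from the study"
- "Is associated with clinical signs or symptoms"
- "Requires treatment or any other therapeutic intervention"
- a link with death or another serious event, hospitalization included
- the investigator's judgement that the clinical impact is significant

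A sixth bullet is a documentation instruction: for a clinically significant result, the investigator describes what was done with the study drug and how the patient fared.

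Section 5.2.2 exempts Grade 4 treatment-related leucopenia, neutropenia and uncomplicated febrile neutropenia from reporting. Section 5.2.1.5 exempts lymphocytopenia of any grade.

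Section 8.1.1 counts an abnormal laboratory finding as an example of an adverse event. Section 8.2.2 asks for a continuing-review table that includes "All Grade 3 and 4 events that are possibly, probably or definitely related to the research", with no condition on symptoms or treatment.

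During each methotrexate cycle, until the drug level is at or below 0.05 mcmol/L, Section 3.8.3.6 requires "CBC with differential daily", daily chemistry, and a hepatic panel every other day. Section 6.1.3 says secondary endpoints are exploratory and does not say which data the toxicity summary uses.

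**The concern.** A description of acute toxicity should rest on a capture rule tied to severity. Here severity plays no part. Two patients with the same Grade 4 value can be handled differently because one had symptoms or was treated and the other was not, or because two investigators judged differently.

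The filter can remove severe values but cannot add any, so whatever bias it causes makes the regimen look better tolerated. That matters because the rationale leans on tolerability. Section 1.2.4.1 describes methotrexate with leucovorin as relatively sparing of the marrow. Section 1.2.4.3 predicts that adding rituximab will not be excessively toxic, and names careful assessment of this as a study objective. The study has a single treatment arm, so no comparison group shares the same under-recording. Accrual is expected to take 6 to 10 years (Section 6.1.3), long enough for discretionary recording to drift.

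**Working it through.** The plan states no toxicity rate or threshold, so there is no figure to reproduce. The check is to set the rules side by side, follow typical values through them, and size one missed patient.

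**1. The rules compared**

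| Section | What qualifies | Depends on grade? |
|---|---|---|
| 5.1 | Laboratory value meeting any one of five conditions | No |
| 5.2.2 | Grade 4 treatment-related leucopenia and neutropenia need not be reported | Yes, as an exemption |
| 8.1.1 | Abnormal laboratory finding is an adverse event | No restriction |
| 8.2.2 | All related Grade 3 and 4 events are tabulated | Yes, as an inclusion |

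A database filtered under 5.1 cannot be relied on to supply the 8.2.2 table. The exemption in 5.2.2 and the inclusion in 8.2.2 also give opposite answers for Grade 4 treatment-related neutropenia, and 8.2.2 does not refer back to 5.2.

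**2. Values followed through 5.1**

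- *Platelets.* Below 50,000/mm³, methotrexate is delayed (3.4.2.6). Without bleeding or a planned procedure, Section 4.9 specifies transfusion only below 10,000/mm³. A count between these two figures can delay chemotherapy while no treatment is given. Recording then depends on investigator judgement, or on whether a delay counts as an intervention, which 5.1 does not say.
- *Neutrophils.* Giving filgrastim meets the treatment condition. It is not routine (3.3.5.1) and is barred after methotrexate until the level is below 0.05 mcmol/L (3.3.5.2.2), which is essentially the period of daily counts. Neutropenia that recovers without it falls to judgement.
- *Transaminases.* At 10 times the upper limit or more, methotrexate is withheld and then reduced (3.4.2.4). Whether a hold or reduction is an intervention is again unstated. Severe values below that threshold that prompt no treatment fall to judgement.
- *Creatinine.* Acute renal injury leads to rescue dosing, hydration and alkalinization (3.4.3), so it should meet the treatment condition.

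**3. Weight of one missed patient**

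- Main cohort of 15: 1/15 = 6.7 percentage points.
- With three replaced patients counted, 15 + 3 = 18: 1/18 = 5.6 points.

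**4. Illustration on assumed rates**

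The documents give neither a true rate nor a recording fraction, so both are assumptions. Apparent rate = true rate × fraction recorded. With a true rate of 40% (15 × 0.40 = 6 patients):

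| Fraction recorded | Expected count of 15 | Apparent rate |
|---|---|---|
| 100% | 6 | 40% |
| 75% | 4.5 | 30% |
| 50% | 3 | 20% |
| 25% | 1.5 | 10% |

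At 50% recording, true rates of 20% to 60% appear as 10% to 30%. Exact 95% intervals are 16.3% to 67.7% for 6 of 15 and 4.3% to 48.1% for 3 of 15. They reflect sampling error only, so they do not correct for values that were never recorded.

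**The case against.** Five alternative conditions apply, and any one suffices. Investigator judgement can capture a value that is neither symptomatic nor treated. The instruction to describe what was done with the study drug shows that the authors had dose-changing values in mind, and a transaminase rise that leads to a hold and a 25% reduction is readily judged significant. Filgrastim or rescue treatment would bring in many other values. Appendix 3 schedules a separate toxicity assessment at each cycle, and nothing confines objective 1.1.2.1 to AE records. Section 5.2 can be read as a deliberate exception to Section 8. The objective is secondary, descriptive and exploratory.

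Much of this stands. A reader might infer that only symptomatic or treated abnormalities are recorded, that severe asymptomatic cytopenias and transaminase rises therefore drop out of the objective, or that every value delaying or reducing methotrexate under 3.4.2 is lost. The documents support none of these. The first overlooks three of the five conditions. The second assumes that AE records are the only source, when the plan is silent. The third ignores judgement and treatment as routes to recording.

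What the objection does not remove is the missing severity criterion. Judgement is still a discretionary filter, the status of a hold or delay is undefined, Appendix 3 does not say what its assessment records, and Sections 5 and 8 still disagree.

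**Conclusion.** The point holds as a gap in the recording rule and an inconsistency between sections, not as demonstrated loss of data. Recording of an asymptomatic, untreated Grade 3-4 laboratory value with no link to discontinuation or a serious event is discretionary under 5.1. For Grade 4 treatment-related leucopenia and neutropenia, reporting is also waived by 5.2.2. Neither fits 8.1.1 and 8.2.2 as written.

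The undercount is conditional on the acute-toxicity summary being drawn from AE records, which the plan neither states nor rules out. Its direction is known (downwards) but its size is not: 6.7 or 5.6 points is the weight of one patient, not an estimate of how many would be missed. The importance is moderate, because the objective is descriptive and the primary two-year endpoint does not depend on laboratory AE records. The change is worth making because it is cheap and removes the discretion.

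**What to change.** Add to Section 5.1 or 6.1.3 that, for objective 1.1.2.1, every laboratory value obtained under the protocol is graded by CTCAE 3.0 directly from the laboratory record, and that the worst grade per patient and per cycle is tabulated for each test whether or not it was entered as an adverse event. State whether replaced patients are in the denominator. The 5.1 conditions can remain for narrative AE entries.

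Reconcile 5.1 and 5.2 with 8.1.1 and 8.2.2. In particular, say whether the 5.2 exemptions apply to the continuing-review table, and whether a methotrexate hold, delay or reduction counts as an intervention under 5.1.

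The cost is a little programming on data already collected. No dose or clinical rule changes. Reported toxicity rates may rise. One limit remains: daily counts stop once methotrexate clears, and the next scheduled count is Day 1 of the following cycle, so a low point in between may still be missed. The hepatic panel, taken every other day, may likewise miss a brief peak. The report should say so.
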